	Moderate	X	XX	xx-xx	X	XX	xx-xx	X	XX	xx-xx	X	XX	xx-xx	X	XX	xx-xx

Table 86: Number and Percentage of Subjects Experiencing Solicited Events by Symptom, Maximum Severity, Treatment Arm and Age Stratum – Post Any Study Vaccination – Safety Population (continued)

		3.75	Group 5 mcg A/ + AS03 (N=X)	H7N9 3	7.5	Group 2 mcg A/H + AS03 (N=X)		15	Group 3 mcg A/H' + AS03 (N=X)		15	Group 4 mcg A/H (N=X)		45	Group 5 mcg A/H (N=X)	; 7N9
Symptom	Severity	n	%	95% CI	n	%	95% CI	n	%	95% CI	n	%	95% CI	n	%	95% CI
	Severe	X	xx	xx-xx	X	XX	xx-xx	Х	XX	xx-xx	X	XX	xx-xx	X	XX	xx-xx
Any Local Symptom	None	X	XX	xx-xx	X	xx	XX-XX	Х	xx	xx-xx	Х	xx	xx-xx	Х	XX	xx-xx
	Mild	X	XX	xx-xx	X	XX	xx-xx	X	XX	xx-xx	X	XX	xx-xx	X	XX	xx-xx
	Moderate	X	XX	xx-xx	X	XX	xx-xx	X	XX	xx-xx	X	XX	xx-xx	X	XX	xx-xx
	Severe	X	XX	xx-xx	X	XX	xx-xx	X	XX	xx-xx	X	XX	xx-xx	X	XX	XX-XX
Pain	None	X	XX	xx-xx	X	XX	xx-xx	X	XX	xx-xx	X	XX	xx-xx	X	XX	xx-xx
	Mild	X	XX	xx-xx	X	XX	xx-xx	X	XX	xx-xx	X	XX	xx-xx	X	XX	xx-xx
	Moderate	X	XX	xx-xx	X	XX	xx-xx	X	XX	xx-xx	X	XX	xx-xx	X	XX	xx-xx
	Severe	X	XX	xx-xx	X	XX	xx-xx	X	XX	xx-xx	X	XX	xx-xx	X	XX	xx-xx
Tenderness	None	X	XX	xx-xx	X	XX	xx-xx	X	XX	xx-xx	X	XX	xx-xx	X	XX	xx-xx
	Mild	X	xx	xx-xx	X	XX	xx-xx	х	XX	xx-xx	Х	XX	xx-xx	X	XX	xx-xx
	Moderate	X	xx	xx-xx	X	XX	xx-xx	Х	XX	xx-xx	X	XX	xx-xx	X	XX	xx-xx
	Severe	X	xx	xx-xx	X	XX	xx-xx	Х	XX	xx-xx	X	XX	xx-xx	X	XX	xx-xx
Pruritus	None	X	xx	xx-xx	X	XX	xx-xx	Х	XX	xx-xx	X	XX	xx-xx	X	XX	xx-xx
	Mild	X	xx	xx-xx	X	XX	xx-xx	Х	XX	xx-xx	X	XX	xx-xx	X	XX	xx-xx
	Moderate	X	XX	xx-xx	X	XX	xx-xx	X	XX	XX-XX	X	XX	xx-xx	X	XX	XX-XX
	Severe	X	xx	xx-xx	X	XX	xx-xx	Х	XX	xx-xx	X	XX	xx-xx	X	XX	xx-xx
Ecchymosis	None	X	xx	xx-xx	X	XX	xx-xx	Х	XX	xx-xx	X	XX	xx-xx	X	XX	xx-xx
	Mild	X	xx	xx-xx	X	XX	xx-xx	Х	XX	xx-xx	X	XX	xx-xx	X	XX	xx-xx
	Moderate	X	XX	xx-xx	X	XX	xx-xx	Х	XX	xx-xx	X	XX	xx-xx	X	XX	xx-xx

Table 86: Number and Percentage of Subjects Experiencing Solicited Events by Symptom, Maximum Severity, Treatment Arm and Age Stratum – Post Any Study Vaccination – Safety Population (continued)

		3.7	Group 5 mcg A/ + AS03 (N=X)	H7N9 3	7.5	Group 2 mcg A/H + AS03 (N=X)	17N9	15	Group 3 mcg A/H + AS03 (N=X)		15	Group 4 mcg A/H (N=X)		45	Group 5 mcg A/H (N=X)	
Symptom	Severity	n	%	95% CI	n	%	95% CI	n	%	95% CI	n	%	95% CI	n	%	95% CI
	Severe	х	XX	xx-xx	X	XX	xx-xx	X	XX	xx-xx	X	XX	xx-xx	X	XX	xx-xx
Ecchymosis (measurement)	None	х	xx	xx-xx	X	XX	XX-XX	X	xx	XX-XX	X	xx	XX-XX	Х	XX	xx-xx
	Mild	X	XX	xx-xx	X	XX	xx-xx	X	XX	xx-xx	X	XX	xx-xx	X	XX	xx-xx
	Moderate	X	XX	xx-xx	X	XX	xx-xx	X	XX	xx-xx	X	XX	xx-xx	X	XX	xx-xx
	Severe	X	XX	xx-xx	X	XX	xx-xx	X	XX	xx-xx	X	XX	xx-xx	X	XX	xx-xx
Erythema	None	X	XX	xx-xx	X	XX	xx-xx	X	XX	xx-xx	X	XX	xx-xx	X	XX	xx-xx
	Mild	Х	XX	xx-xx	X	XX	xx-xx	X	XX	xx-xx	X	XX	xx-xx	X	XX	xx-xx
	Moderate	X	XX	xx-xx	X	XX	xx-xx	X	XX	xx-xx	X	XX	xx-xx	X	XX	xx-xx
	Severe	х	XX	xx-xx	X	XX	xx-xx	X	xx	xx-xx	X	xx	xx-xx	Х	XX	xx-xx
Erythema (measurement)	None	Х	xx	xx-xx	X	XX	XX-XX	X	xx	XX-XX	X	xx	XX-XX	X	XX	xx-xx
	Mild	Х	XX	xx-xx	X	XX	xx-xx	X	XX	xx-xx	X	XX	xx-xx	X	XX	xx-xx
	Moderate	Х	XX	xx-xx	X	XX	xx-xx	X	XX	xx-xx	X	XX	xx-xx	X	XX	xx-xx
	Severe	х	XX	xx-xx	X	XX	xx-xx	X	XX	xx-xx	X	XX	xx-xx	X	XX	xx-xx
Induration/Swelling	None	Х	XX	xx-xx	X	XX	xx-xx	X	XX	xx-xx	X	XX	xx-xx	X	XX	xx-xx
	Mild	X	XX	xx-xx	X	XX	xx-xx	X	XX	xx-xx	X	XX	xx-xx	X	XX	xx-xx
	Moderate	X	XX	xx-xx	X	XX	xx-xx	X	XX	xx-xx	X	XX	xx-xx	X	XX	xx-xx
	Severe	х	XX	xx-xx	Х	XX	xx-xx	X	XX	xx-xx	X	XX	xx-xx	X	XX	XX-XX
Induration/Swelling (measurement)	None	х	xx	xx-xx	X	XX	XX-XX	X	xx	XX-XX	X	xx	xx-xx	X	XX	xx-xx
	Mild	Х	XX	xx-xx	X	XX	xx-xx	X	XX	xx-xx	X	XX	xx-xx	X	XX	xx-xx

Table 86: Number and Percentage of Subjects Experiencing Solicited Events by Symptom, Maximum Severity, Treatment Arm and Age Stratum – Post Any Study Vaccination – Safety Population (continued)

		3.75	Group 1 5 mcg A/l + AS03 (N=X)	H7N9	7.5	Group 2 mcg A/H + AS03 (N=X)		15	Group 3 mcg A/H' + AS03 (N=X)		15	Group 4 mcg A/H' (N=X)		45 1	Group 5 mcg A/H' (N=X)	
Symptom	Severity	n	%	95% CI	n	%	95% CI	n	%	95% CI	n	%	95% CI	n	%	95% CI
	Moderate	X	XX	xx-xx	X	XX	xx-xx	X	XX	xx-xx	X	XX	xx-xx	X	XX	xx-xx
	Severe	X	XX	xx-xx	X	XX	XX-XX	X	XX	xx-xx	X	XX	XX-XX	X	XX	xx-xx

N = Number of subjects in the Safety Population who received any study vaccination.

^{95%} CI estimated using Clopper-Pearson exact method

Severity is the maximum severity reported over all solicited symptoms post dosing for each subject.

Table 87: Number and Percentage of Subjects Experiencing Solicited Events by Symptom, Maximum Severity, Treatment Arm and Age Stratum Post Study Vaccination 1 – Safety Population *

[Footnote Update] N = Number of subjects in the Safety Analysis Population who received the first study vaccination.

Table 88: Number and Percentage of Subjects Experiencing Solicited Events by Symptom, Maximum Severity, Treatment Arm and Age Stratum Post Study Vaccination 2 – Safety Population *

[Footnote Update] N = Number of subjects in the Safety Analysis Population who received the second study vaccination.

Table 89: Number and Percentage of Subjects Experiencing Solicited Events by Symptom, Severity, Day Post Study Vaccination, Treatment Arm and Age Stratum Post Any Study Vaccination – Safety Population

Crimitan	Severity	Dwa	-Vac.		ost- ac.	Ъ	1	D	y 2	D.	2	D.	ıy 4	D	ıy 5	D.	ny 6	D.	7	D-	y 8+
Symptom	Severity	n	-vac.	n	ac.	-	ay 1 %	n	y 2 %	n	y 3	n	1y 4 %	n	ly 5 %	n	1y 6 %	n	y 7 %	n	y 8+ %
		11		 	 		1	 	AS03 ( 		11	/0	_ 11	/0		/0		/0		/0
All Subjects			G	Toup	1. 5.	75 IIIC	g M/II	7117	1505	(11 21)	,										
Any Symptom	None																				
7 my Symptom	Mild																				
	Moderate																				
	Severe																				
Any Systemic Symptom	None																				
	Mild																				
	Moderate																				
	Severe																				
Fever	None																				
	Mild																				
	Moderate																				
	Severe																				
Feverishness	None																				
	Mild																				
	Moderate																				
	Severe																				
Fatigue	None																				
	Mild																				
	Moderate																				
	Severe																				
Malaise	None																				

Table 89: Number and Percentage of Subjects Experiencing Solicited Events by Symptom, Severity, Day Post Study Vaccination, Treatment Arm and Age Stratum – Post Any Study Vaccination – Safety Population (continued)

Symptom	Severity	Pre	-Vac.	Po V	ost- ac.	Da	ay 1	Da	ay 2	Da	ıy 3	Da	ay 4	Da	ny 5	Da	ıy 6	Da	ny 7	Da	y 8+
		n	%	n	%	n	%	n	%	n	%	n	%	n	%	n	%	n	%	n	%
	Mild																				
	Moderate																				
	Severe																				
Myalgia	None																				
	Mild																				
	Moderate																				
	Severe																				
Arthralgia	None																				
	Mild																				
	Moderate																				
	Severe																				
Headache	None																				
	Mild																				
	Moderate																				
	Severe																				
Nausea	None																				
	Mild																				
	Moderate																				
	Severe																				
Any Local Symptom	None																				
	Mild																				
	Moderate																				
	Severe																				

Table 89: Number and Percentage of Subjects Experiencing Solicited Events by Symptom, Severity, Day Post Study Vaccination, Treatment Arm and Age Stratum – Post Any Study Vaccination – Safety Population (continued)

Symptom	Severity	Pre	-Vac.	Po V	ost- ac.	Da	ay 1	Da	ny 2	Da	ıy 3	Da	ıy 4	Da	ny 5	Da	ny 6	Da	ıy 7	Da	y 8+
		n	%	n	%	n	%	n	%	n	%	n	%	n	%	n	%	n	%	n	%
Pain	None																				
	Mild																				
	Moderate																				
	Severe																				
Tenderness	None																				
	Mild																				
	Moderate																				
	Severe																				
Pruritus	None																				
	Mild																				
	Moderate																				
	Severe																				
Ecchymosis	None																				
	Mild																				
	Moderate																				
	Severe																				
Ecchymosis (measurement)	None																				
	Mild																				
	Moderate																				
	Severe																				
Erythema	None																				
	Mild																				
	Moderate																				

Table 89: Number and Percentage of Subjects Experiencing Solicited Events by Symptom, Severity, Day Post Study Vaccination, Treatment Arm and Age Stratum – Post Any Study Vaccination – Safety Population (continued)

Symptom	Severity	Pre	-Vac.		ost- ac.	Da	ay 1	Da	ıy 2	Da	y 3	Da	ıy 4	Da	ıy 5	Da	ıy 6	Da	ıy 7	Day	y 8+
		n	%	n	%	n	%	n	%	n	%	n	%	n	%	n	%	n	%	n	%
	Severe																				
Erythema (measurement)	None																				
	Mild																				
	Moderate																				
	Severe																				
Induration/Swelling	None																				
	Mild																				
	Moderate																				
	Severe																				
Induration/Swelling (measurement)	None																				
	Mild																				
	Moderate																				
	Severe																				

[Repeat for Ages 19-64 and \geq 65]

[repeat for all treatment arms]

N = Number of subjects in the Safety Analysis Population who received any study vaccination. Severity is the maximum severity reported post dosing for each subject for each day.

Table 90: Number and Percentage of Subjects Experiencing Solicited Events by Symptom, Severity, Day Post Study Vaccination, Treatment Arm and Age Stratum Post Study Vaccination 1 – Safety Population

Footnote update: N = Number of subjects in the Safety Analysis Population who received the first study vaccination.

Table 91: Number and Percentage of Subjects Experiencing Solicited Events by Symptom, Severity, Day Post Study Vaccination, Treatment Arm and Age Stratum Post Study Vaccination 2 – Safety Population

Footnote update: N = Number of subjects in the Safety Analysis Population who received the second study vaccination.

Table 92: Number and Percentage of Subjects Experiencing Solicited Systemic Events for Dose 1 Compared with Dose 2 by Treatment Arm and Age Stratum – Safety Population

				Study Vaccination 2	
Treatment Arm	Age Stratum	Study Vaccination 1	Subjects with No Symptoms	Subjects with Mild or Greater Symptoms	Total Number of Subjects n (Percent) [p-value*]
Group 1 3.75 mcg	Ages 19-64	Subjects with No Symptoms	x (%)	x (%)	x (%)
A/H7N9 + AS03		Subjects with Mild or Greater Symptoms	x (%)	x (%)	x (%)
		Total Number of Subjects	x (%)	x (%)	x (100%) [0.xxx]
	Ages ≥ 65	Subjects with No Symptoms	x (%)	x (%)	x (%)
		Subjects with Mild or Greater Symptoms	x (%)	x (%)	x (%)
		Total Number of Subjects	x (%)	x (%)	x (100%) [0.xxx]
	All Subjects	Subjects with No Symptoms	x (%)	x (%)	x (%)
		Subjects with Mild or Greater Symptoms	x (%)	x (%)	x (%)
		Total Number of Subjects	x (%)	x (%)	x (100%) [0.xxx]
Group 2 7.5 mcg	Ages 19-64	Subjects with No Symptoms	x (%)	x (%)	x (%)
A/H7N9 + AS03		Subjects with Mild or Greater Symptoms	x (%)	x (%)	x (%)
		Total Number of Subjects	x (%)	x (%)	x (100%) [0.xxx]
	Ages ≥ 65	Subjects with No Symptoms	x (%)	x (%)	x (%)
		Subjects with Mild or Greater Symptoms	x (%)	x (%)	x (%)

Table 92: Number and Percentage of Subjects Experiencing Solicited Systemic Events for Dose 1 Compared with Dose 2 by Treatment Arm and Age Stratum – Safety Population (continued)

				Study Vaccination 2	
Treatment Arm	Age Stratum	Study Vaccination 1	Subjects with No Symptoms	Subjects with Mild or Greater Symptoms	Total Number of Subjects n (Percent) [p-value*]
		Total Number of Subjects	x (%)	x (%)	x (100%) [0.xxx]
	All Subjects	Subjects with No Symptoms	x (%)	x (%)	x (%)
		Subjects with Mild or Greater Symptoms	x (%)	x (%)	x (%)
		Total Number of Subjects	x (%)	x (%)	x (100%) [0.xxx]
Group 3 15 mcg	Ages 19-64	Subjects with No Symptoms	x (%)	x (%)	x (%)
A/H7N9 + AS03		Subjects with Mild or Greater Symptoms	x (%)	x (%)	x (%)
		Total Number of Subjects	x (%)	x (%)	x (100%) [0.xxx]
	Ages ≥ 65	Subjects with No Symptoms	x (%)	x (%)	x (%)
		Subjects with Mild or Greater Symptoms	x (%)	x (%)	x (%)
		Total Number of Subjects	x (%)	x (%)	x (100%) [0.xxx]
	All Subjects	Subjects with No Symptoms	x (%)	x (%)	x (%)
		Subjects with Mild or Greater Symptoms	x (%)	x (%)	x (%)
		Total Number of Subjects	x (%)	x (%)	x (100%) [0.xxx]
	Ages 19-64	Subjects with No Symptoms	x (%)	x (%)	x (%)

Table 92: Number and Percentage of Subjects Experiencing Solicited Systemic Events for Dose 1 Compared with Dose 2 by Treatment Arm and Age Stratum – Safety Population (continued)

				Study Vaccination 2	
Treatment Arm	Age Stratum	Study Vaccination 1	Subjects with No Symptoms	Subjects with Mild or Greater Symptoms	Total Number of Subjects n (Percent) [p-value*]
Group 4 15 mcg		Subjects with Mild or Greater Symptoms	x (%)	x (%)	x (%)
A/H7N9		Total Number of Subjects	x (%)	x (%)	x (100%) [0.xxx]
	Ages ≥ 65	Subjects with No Symptoms	x (%)	x (%)	x (%)
		Subjects with Mild or Greater Symptoms	x (%)	x (%)	x (%)
		Total Number of Subjects	x (%)	x (%)	x (100%) [0.xxx]
	All Subjects	Subjects with No Symptoms	x (%)	x (%)	x (%)
		Subjects with Mild or Greater Symptoms	x (%)	x (%)	x (%)
		Total Number of Subjects	x (%)	x (%)	x (100%) [0.xxx]
Group 5 45 mcg	Ages 19-64	Subjects with No Symptoms	x (%)	x (%)	x (%)
A/H7N9		Subjects with Mild or Greater Symptoms	x (%)	x (%)	x (%)
		Total Number of Subjects	x (%)	x (%)	x (100%) [0.xxx]
	Ages ≥ 65	Subjects with No Symptoms	x (%)	x (%)	x (%)
		Subjects with Mild or Greater Symptoms	x (%)	x (%)	x (%)
		Total Number of Subjects	x (%)	x (%)	x (100%) [0.xxx]

Table 92: Number and Percentage of Subjects Experiencing Solicited Systemic Events for Dose 1 Compared with Dose 2 by Treatment Arm and Age Stratum – Safety Population (continued)

			Study Vaccination 2							
Treatment Arm	Age Stratum	Study Vaccination 1	Subjects with No Symptoms	Subjects with Mild or Greater Symptoms	Total Number of Subjects n (Percent) [p-value*]					
	All Subjects	Subjects with No Symptoms	x (%)	x (%)	x (%)					
		Subjects with Mild or Greater Symptoms	x (%)	x (%)	x (%)					
		Total Number of Subjects	x (%)	x (%)	x (100%) [0.xxx]					

Note: Denominators for percentages are the number of subjects in the safety population who received both the first and second study vaccination. [x] subjects did not get the second dose and are not included in this table.

Table with similar format:

Table 93: Number and Percentage of Subjects Experiencing Solicited Local Events for Dose 1 Compared with Dose 2 by Treatment Arm and Age Stratum – Safety Population

^{*} P-value is calculated from McNemar's test for each group and age stratum pair.

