11.6.2 Safety Data

Summaries and analysis of safety data will be presented for the Safety Analysis Population. All summaries and analyses will be presented for all subjects, and by age stratum.

Solicited AEs will be summarized by severity for each day after each study vaccination (Days 1-7 post each study vaccination) and as the maximum severity over all 8 days. Additionally, solicited AEs will be analyzed by taking the most severe response over the follow-up period, dichotomizing into a binary variable (none versus mild, moderate, or severe) and using standard techniques, such as exact confidence intervals, to summarize the proportion of subjects reporting each symptom, any injection site symptom, and any systemic symptom. Summaries of solicited AEs will be presented separately for each study vaccination as well as overall study vaccinations by treatment arm. The proportion of subjects reporting symptoms may be compared between

treatment arms using Chi-square or Fisher's exact test. The proportion of subjects reporting solicited symptoms between the different study vaccinations (i.e., first and second) will be compared using McNemar's test.

Unsolicited AEs will be coded by Medical Dictionary for Regulatory Activities (MedDRA®) for preferred term and system organ class (SOC). The numbers of SAEs, MAAEs, including NOCMCs, and PIMMCs are likely to be small in this trial and will be reported by detailed listings showing the event description, MedDRA® preferred term and SOC, relevant dates (study vaccinations and AEs), severity, relatedness, and outcome for each event. Non-serious unsolicited AEs will be summarized as number and percentage of subjects reporting at least one event in each MedDRA® preferred term and SOC, cross tabulated by severity and relationship to study product. Additionally, the proportion of subjects and exact 95% confidence intervals of AEs in aggregate and by MedDRA® categories will be computed.

Clinical laboratory data will be summarized by severity for each visit and as the maximum over all post-study vaccination visits. Graphical presentations may include box plots.

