3.2. Endpoints

3.2.1. Primary

Safety:

- Occurrence of study vaccine-related serious adverse events (SAEs) from the time of the first study vaccination through approximately 12 months after the last study vaccination.
- Occurrence of solicited injection site and systemic reactogenicity events from the time of each study vaccination through 7 days after each study vaccination.
- Occurrence of clinical safety laboratory adverse events from the time of each study vaccination through approximately 7 days after each study vaccination.

Immunogenicity:

- For HAI and Neut antibodies, percentage of subjects achieving seroconversion against the influenza 2017 H7N9 study vaccine strain (defined as either a prevaccination titer <1:10 and a post-vaccination titer ≥1:40 or a pre-vaccination titer ≥1:10 and a minimum four-fold rise in post-vaccination titer) at approximately 21 days after the second study vaccination (Study Day 43).
- For HAI and Neut antibodies, percentage of subjects achieving titer ≥1:40 against the influenza 2017 H7N9 study vaccine strain at approximately 21 days after the second study vaccination (Study Day 43).
- Geometric Mean Titers (GMTs) of serum HAI and Neut antibodies against the influenza 2017 H7N9 vaccine strain at approximately 21 days after the second study vaccination (Study Day 43).

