9.3.1. Solicited Events and Symptoms

Systemic solicited adverse events were collected pre-vaccination, and systemic and local solicited adverse events were collected at-least 20 minutes post-vaccination and then daily for 7 days after each vaccination and graded on a scale of 0 (absent), 1 (mild), 2 (moderate) and 3 (severe). Systemic events include fever, feverishness, fatigue, malaise, myalgia, arthralgia, headache, and nausea. The grading scale for systemic events, including quantitative grading for fever, is included in Table 11. Local events include pruritus, ecchymosis, erythema, induration/swelling, pain, and tenderness. Ecchymosis, erythema, and induration are measured by both functional and measurement grading scales as defined in Table 10.

When calculating the incidence of solicited events, each subject will be counted once at the highest severity following the applicable vaccination, and any repetitions will be ignored. For summaries presented separately for each vaccination, the denominator for percentages will be the number of subjects who received the respective vaccination with non-missing data for the event summarized. For summaries over all vaccinations the denominator will be the number of subjects who received at least one vaccination with non-missing data for the event summarized.

The number and percentage of subjects reporting at least one solicited adverse event of any severity will be summarized for each solicited symptom, any systemic symptom, any local symptom, and any symptoms. For each event the denominator is the number of subjects who received the applicable vaccination with non-missing data for the specific event. The 95% CI calculated using Clopper-Pearson methodology from a binomial distribution (SAS Proc Freq with a binomial option) will be presented (Table 75, Table 76, Table 77, Table 78, Table 79, and Table 80). Logistic regression models will be fit to estimate the effect of treatment and age on the probability of reporting any local event or reporting any systemic event (Table 81 and Table 82). If statistically significant effects are observed in the model for local events or systemic events, then additional models will be fit for each individual event of that type.

$$logit[P(Event)] = \beta_0 + \beta_1 \times Treatment + \beta_2 (Age \ge 65) + \varepsilon,$$

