For each systemic and local event, any systemic event, any local event, and any solicited event, the maximum severity over 7 days after each vaccination will be summarized for the Safety population. The number and percentage of subjects reporting each event will be summarized by the maximum severity and treatment group overall and by age stratum, separately for each vaccination and over all vaccinations. For each event the denominator is the number of subjects who received the applicable vaccination with non-missing data for the specific event. The 95% CI calculated using Clopper-Pearson methodology from a binomial

distribution (SAS Proc Freq with a binomial option) will be presented (Table 83, Table 84, Table 85, Table 86, Table 87, and Table 88).

The number of subjects reporting a solicited adverse event will be summarized for each day post vaccination for each vaccination and for all vaccinations combined both in a summary table (Table 89, Table 90, and Table 91) and graphically in a bar chart (Figure 19 and Figure 20). A comparison of the event rate for each treatment group between vaccination 1 and vaccination 2 will be presented, including p-values from McNemar's test performed within each age stratum and over all subject (Table 92 and Table 93).

Systemic and Local solicited events reported by subject will be presented in Listing 9 and Listing 10, sorted by subject ID, vaccination number, parameter, and study day.

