Table 80: Number and Percentage of Subjects Experiencing Solicited Events with 95% Confidence Intervals by Symptom, Treatment Arm and Age Stratum Post Study Vaccination 2 – Safety Population *

[Footnote update] N = Number of subjects in the Safety Population who received the second vaccination.

Table 81: Logistic Regression Model to Evaluate the Relationship of HA Antigen Dose, AS03 Adjuvant, and Age with Reporting Any Local Event Post Any Study Vaccination – Safety Population *

Model Parameter	Parameter Levels	Parameter Estimate	SE	p-value	Odds Ratio	95%CI
Intercept	-	xxx.x	xxx.x	x.xxx	-	-
Freatment	3.75 mcg with AS03 adjuvant (reference)	-	-	-	-	-
	7.5 mcg with AS03 adjuvant	xxx.x	xxx.x	x.xxx	xx.x	xx.x-xx.x
	15 mcg with AS03 adjuvant	XXX.X	xxx.x	x.xxx	XX.X	XX.X-XX.X
	15 mcg without AS03 adjuvant	XXX.X	xxx.x	x.xxx	xx.x	XX.X-XX.X
	45 mcg without AS03 adjuvant	xxx.x	xxx.x	x.xxx	xx.x	xx.x-xx.x
Age	19-64 years (reference)	-	-	-	-	-
	≥65 years	XXX.X	xxx.x	x.xxx	xx.x	XX.X-XX.X
Interaction (Age * Treatment)	≥65 years * 7.5 mcg with AS03 adjuvant	XXX.X	XXX.X	x.xxx	XX.X	xx.x-xx.x
	≥65 years * 15 mcg with AS03 adjuvant	XXX.X	xxx.x	x.xxx	XX.X	XX.X-XX.X
	≥65 years * 15 mcg without AS03 adjuvant	XXX.X	xxx.x	x.xxx	XX.X	XX.X-XX.X
	≥65 years * 45 mcg without AS03 adjuvant	XXX.X	XXX.X	x.xxx	XX.X	xx.x-xx.x

N = XX subjects in the safety population.

P-value for Treatment = 0.XXX; P-value for Age = 0.XXX; P-value for interaction of Treatment and Age = 0.XXX.

Table with similar format:

Table 82: Logistic Regression Model to Evaluate the Relationship of HA Antigen Dose, AS03 Adjuvant, and Age with Reporting Any Systemic Event Post Any Study Vaccination (N=X) – Safety Population *

Table 83: Number and Percentage of Subjects Experiencing Solicited Events by Symptom, Maximum Severity and Treatment Arm Post Any Study Vaccination – Safety Population *

		3.75	Group 1 mcg A/I + AS03 (N=X)	H7N9		Group 2 mcg A/H + AS03 (N=X)			Group 3 mcg A/H + AS03 (N=X)	7N9		Group 4 mcg A/H (N=X)			Group : mcg A/H (N=X)	17N9
Symptom	Severity	n	%	95% CI	n	%	95% CI	n	%	95% CI	n	%	95% CI	n	%	95% CI
Any Symptom	None	Х	XX	xx-xx	х	XX	xx-xx	X	XX	xx-xx	х	XX	xx-xx	X	XX	xx-xx
	Mild	х	XX	xx-xx	X	XX	xx-xx	X	XX	xx-xx	X	XX	xx-xx	X	XX	xx-xx
	Moderate	х	xx	xx-xx	X	XX	xx-xx	X	xx	xx-xx	Х	xx	xx-xx	Х	XX	xx-xx
	Severe	х	xx	xx-xx	X	XX	xx-xx	X	xx	xx-xx	Х	xx	xx-xx	Х	XX	xx-xx
Any Systemic Symptom	None	Х	xx	xx-xx	Х	xx	xx-xx	X	xx	xx-xx	х	XX	XX-XX	Х	XX	xx-xx
	Mild	X	XX	xx-xx	X	XX	xx-xx	X	XX	xx-xx	X	XX	xx-xx	X	XX	xx-xx

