Symptom	Severity	n	%	95% CI	n	%	95% CI	n	%	95% CI	n	%	95% CI	n	%	95% CI
Erythema	None	х	XX	xx-xx	X	XX	xx-xx	X	XX	xx-xx	х	XX	xx-xx	X	XX	xx-xx
	Mild	х	xx	xx-xx	Х	XX	xx-xx	Х	XX	xx-xx	х	xx	xx-xx	Х	XX	xx-xx
	Moderate	х	xx	xx-xx	X	xx	xx-xx	X	XX	xx-xx	х	xx	xx-xx	X	XX	xx-xx
	Severe	х	XX	xx-xx	X	XX	xx-xx	X	XX	xx-xx	х	XX	xx-xx	X	XX	xx-xx
Erythema (measurement)	None	х	XX	xx-xx	X	xx	xx-xx	х	XX	xx-xx	Х	XX	XX-XX	Х	XX	XX-XX
	Mild	х	XX	xx-xx	X	XX	xx-xx	X	XX	xx-xx	х	XX	xx-xx	X	XX	xx-xx
	Moderate	х	XX	xx-xx	X	XX	xx-xx	X	XX	xx-xx	х	XX	xx-xx	X	XX	xx-xx
	Severe	х	XX	xx-xx	X	XX	xx-xx	X	XX	xx-xx	х	XX	xx-xx	X	XX	xx-xx
Induration/Swelling	None	х	XX	xx-xx	X	XX	xx-xx	X	XX	xx-xx	х	XX	xx-xx	X	XX	xx-xx
	Mild	х	XX	xx-xx	X	XX	xx-xx	X	XX	xx-xx	х	XX	xx-xx	X	XX	xx-xx
	Moderate	Х	xx	xx-xx	X	XX	xx-xx	х	XX	xx-xx	х	XX	xx-xx	х	XX	xx-xx
	Severe	X	XX	xx-xx	X	XX	xx-xx	X	XX	xx-xx	х	XX	xx-xx	X	XX	xx-xx
Induration/Swelling (measurement)	None	Х	XX	XX-XX	X	XX	xx-xx	X	XX	xx-xx	Х	XX	xx-xx	X	XX	xx-xx
	Mild	х	xx	xx-xx	X	XX	xx-xx	X	xx	xx-xx	х	XX	xx-xx	X	XX	xx-xx
	Moderate	х	xx	xx-xx	X	XX	xx-xx	X	xx	xx-xx	х	XX	xx-xx	X	XX	xx-xx
	Severe	Х	xx	xx-xx	X	XX	xx-xx	х	xx	xx-xx	х	XX	xx-xx	х	XX	xx-xx

N = Number of subjects in the Safety Population who received any study vaccination.

Severity is the maximum severity reported over all solicited symptoms post dosing for each subject.

^{95%} CI estimated using Clopper-Pearson exact method

Table 84: Number and Percentage of Subjects Experiencing Solicited Events by Symptom, Maximum Severity and Treatment Arm Post Study Vaccination 1 – Safety Population *

[Footnote Update] N = Number of subjects in the Safety Analysis Population who received the first study vaccination.

Table 85: Number and Percentage of Subjects Experiencing Solicited Events by Symptom, Maximum Severity and Treatment Arm Post Study Vaccination 2 – Safety Population *

[Footnote Update] N = Number of subjects in the Safety Analysis Population who received the second study vaccination.

Table 86: Number and Percentage of Subjects Experiencing Solicited Events by Symptom, Maximum Severity, Treatment Arm and Age Stratum Post Any Study Vaccination – Safety Population *

		3.75	Group 5 mcg A/2 + AS03 (N=X)	H7N9 3	7.5	Group 2 mcg A/H + AS03 (N=X)		15	Group 3 mcg A/H + AS03 (N=X)		15	Group 4 mcg A/H' (N=X)		45	Group 5 mcg A/H (N=X)	; 7N9
Symptom	Severity	n	%	95% CI	n	%	95% CI	n	%	95% CI	n	%	95% CI	n	%	95% CI
							Age 19	-64								•
Any Symptom	None	X	XX	xx-xx	X	XX	xx-xx	X	xx	xx-xx	X	XX	xx-xx	X	XX	xx-xx

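### The footnote to SAP Tables 83 to 88 grades every row by the subject's worst solicited symptom, which suits only the Any Symptom row and contradicts SAP 9.3.1

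*SAP*

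**What the plan says.** Table 83 in SAP Appendix 1 is titled "Number and Percentage of Subjects Experiencing Solicited Events by Symptom, Maximum Severity and Treatment Arm Post Any Study Vaccination"; Table 86 is the version by age stratum. Each has 20 rows (in Table 86, per stratum): Any Symptom, Any Systemic Symptom, Any Local Symptom, eight systemic symptoms, and nine local rows (six symptoms, three of them repeated with a measurement grade). Each row is split into None, Mild, Moderate and Severe.

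The footnote to both tables states: "Severity is the maximum severity reported over all solicited symptoms post dosing for each subject". Tables 84, 85, 87 and 88 have the same format for vaccination 1 or vaccination 2 alone. Their only footnote change is to N, so the severity line carries over.

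The text of SAP 9.3.1 sets a different rule and cites Tables 83 to 88 for it: "For each systemic and local event, any systemic event, any local event, and any solicited event, the maximum severity over 7 days after each vaccination". An earlier sentence of the same section says that "each subject will be counted once at the highest severity following the applicable vaccination", which by itself fits either rule.

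Protocol 11.6.2 asks for the maximum severity of solicited events over the follow-up days and, after dichotomising, for exact methods "to summarize the proportion of subjects reporting each symptom, any injection site symptom, and any systemic symptom".

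**The concern.** A subject's row entry should be the worst grade of the event that the row names. The footnote instead gives the subject's worst grade across all solicited symptoms. Take an invented subject with Grade 3 fatigue, Grade 1 headache and no nausea. Under SAP 9.3.1 the entries are severe fatigue, mild headache and no nausea. Under the footnote this subject is severe in all three rows, and in the local rows as well.

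Solicited reactogenicity is a primary safety outcome, and all six tables are marked for the Preliminary Report. SAP 6.2.2 treats analyses in that report as final for those data and allows their release to the lead investigator for publication. A wrong grade would therefore reach the published severity profile. Correct programming under this footnote would still publish a definition that does not describe the numbers above it.

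**Working it through.** **1. Footnote against SAP 9.3.1, row by row**

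| Rows | Number | Maximum under 9.3.1 | Maximum under the footnote | Agree? |
|---|---|---|---|---|
| Any Symptom | 1 | all solicited symptoms | all solicited symptoms | yes |
| Any Systemic, Any Local | 2 | symptoms of that class | all solicited symptoms | no |
| Single symptoms (8 systemic, 9 local) | 17 | that symptom | all solicited symptoms | no |

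The count is 17 + 2 = 19 rows in disagreement out of 17 + 2 + 1 = 20.

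Neighbouring shells do not pool in this way. The footnote to Table 89 takes the maximum per subject per day and does not mention all symptoms. The note to Figure 19 pools only across systemic events.

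**2. Direction**

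A maximum over all symptoms is never below the maximum over one of them. The severe share in a row can therefore only stay the same or rise.

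**3. Size**

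The plan gives no severe rate, between-symptom correlation or inflation figure, so there is nothing to reproduce. The following shows only what the size depends on.

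Let p_j be the true severe rate of symptom j and k the number of symptoms. Under the literal footnote, every row's severe share equals P(any severe), and row j is inflated by P(any severe) / p_j.

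- Independent symptoms: P(any severe) = 1 − ∏(1 − p_j).
- Latent correlation ρ (equicorrelated normal model): P(any severe) = 1 − ∫ ∏ Φ((t_j − √ρ·z)/√(1 − ρ)) φ(z) dz, with t_j = Φ⁻¹(1 − p_j).

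With one common rate the first formula has the form behind Protocol Table 3. At 1% it gives 45.3, 63.4, 80.0 and 99.2% for N = 60, 100, 160 and 480, against the printed 45, 63, 80 and >99.

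For k = 14 distinct symptoms, with all rates and correlations **assumed**:

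| Assumed severe rates | Quantity | ρ = 0 | ρ = 0.5 | ρ = 0.7 | ρ = 0.9 |
|---|---|---|---|---|---|
| All 14 at 1% | P(any severe) | 13.1% | 8.4% | 5.9% | 3.2% |
| | inflation, every symptom | 13.1 | 8.4 | 5.9 | 3.2 |
| One at 5%, thirteen at 1% | P(any severe) | 16.6% | 10.9% | 8.2% | 5.5% |
| | inflation, commonest | 3.3 | 2.2 | 1.6 | 1.1 |
| | inflation, rarer | 16.6 | 10.9 | 8.2 | 5.5 |
| One at 10%, thirteen at 1% | P(any severe) | 21.0% | 14.6% | 12.0% | 10.1% |
| | inflation, commonest | 2.1 | 1.5 | 1.2 | 1.0 |
| | inflation, rarer | 21.0 | 14.6 | 12.0 | 10.1 |

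For example, 1 − 0.99^14 = 13.1%, and 1 − 0.90 × 0.99^13 = 21.0%. With equal rates and full correlation the inflation is exactly 1.

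**4. A partial reading of the footnote**

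A programmer might leave subjects without the symptom in None and give those who report it their overall worst grade. The severe share is then P(symptom present and any symptom severe). This lies between p_j and P(any severe), so step 3 gives its upper limit.

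**The case against.** The strongest reply is that the SAP already states the correct rule. Section 9.3.1 cites these tables, their titles say by symptom, and each symptom has its own severity levels. Applied literally, the footnote would make all 20 rows identical, and their None counts would clash with the any-grade incidences in Tables 75 to 80. It looks like an any-symptom footnote left in place. Most of this stands, and it is why the point is minor. It does not remove the conflict. Under the partial reading in step 4, the rows differ and their None counts agree with Tables 75 to 80, so those checks would not catch the error.

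A reader might infer more than the documents support:

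- **An unlimited or inconsistent time window.** The footnote says only post dosing and names no limit, but solicited events are collected through 7 days after each dose. The protocol's "as the maximum severity over all 8 days" can be the same window: the vaccination day plus 7 days makes 8 calendar days. The open-ended Day 8+ column belongs to Tables 89 to 91 and sets no rule for the maximum here.
- **Failure of the primary outcome.** That outcome is "Occurrence of solicited injection site and systemic reactogenicity events from the time of each study vaccination through 7 days after each study vaccination". Any-grade occurrence is in Tables 75 to 80, which do not carry this footnote.
- **Distortion between arms.** Protocol 2.3.1 reports higher incidence and severity of local reactions with AS03, but no data on how often symptoms occur together. Under the literal rule with equal rates, stronger correlation lowers the inflation (13.1-fold at ρ = 0, 3.2-fold at ρ = 0.9). No direction can be asserted.
- **A direct conflict with the protocol.** Protocol 11.6.2 does not say whether the maximum is taken within a symptom or across symptoms. Its per-symptom wording concerns the dichotomised proportions. The clear contradiction is within the SAP.

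**Conclusion.** The footnote is wrong as written for 19 of 20 rows in each of Tables 83 to 88 (per stratum in the age tables) and contradicts SAP 9.3.1. That finding needs no assumption. Any numerical error depends on the footnote being programmed in preference to 9.3.1, which is possible but not shown. In that case single-symptom severe rates would be overstated, or at best unchanged. The inflation would be close to 1-fold for a symptom that accounts for nearly all severe reports, or for symptoms of similar frequency that become severe almost always together. It would be several-fold or more for rarer symptoms. A reader might conclude that the published rates will be several times too high; the documents support neither that certainty nor any particular multiple. The point is minor: a definition to correct before the tables are issued, not a demonstrated bias.

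**What to change.** Replace the severity line in the footnotes of Tables 83 to 88 with:

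*Severity is the maximum grade reported for the event named in the row (for the Any Systemic, Any Local and Any Symptom rows, the maximum over the symptoms in that class) from vaccination through 7 days after the applicable study vaccination(s).*

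For Tables 83 and 86 add that the maximum is taken over the windows of both vaccinations. In Tables 84, 85, 87 and 88 it is taken over the window of the one vaccination named in the title. State the line explicitly in those four shells rather than leaving it to be inherited.

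The cost is one footnote. It needs no new data, no change to SAP 9.3.1 and no change to any other table.
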